### **6.7.2 Instruction for prescribing and taking study treatment**

Eltrombopag will be administered orally, once daily, on an empty stomach (1 hour before or 2 hours after a meal) and at least 2 hours before or 4 hours after any products containing polyvalent cations such as antacids, calcium-rich foods ( $> 50$  mg calcium, e.g., dairy products and calcium-fortified juices), or mineral supplements containing polyvalent cations (e.g. aluminum, calcium, iron, magnesium, selenium, and zinc).

Subjects will be instructed to take eltrombopag daily at the same time each day.

On days that PK samples are obtained, the subject should take eltrombopag during the clinic visit after the pre-dose PK samples and prior to post-dose PK samples, when instructed by the study staff.

If vomiting occurs during the course of treatment, subjects should not take the study drug (eltrombopag) again before the next scheduled dose.

Subjects will be instructed not to make up missed doses. A missed dose is defined as a case when the full dose is not taken within 8 hours of the approximate time of the usual daily dose. That day's dose should be omitted and the subject should continue treatment with the next scheduled dose.

## **7 Informed consent procedures**

Eligible subjects may only be included in the study after providing (witnessed, where required by law or regulation), IRB/IEC-approved informed consent.

If applicable, in cases where the subject's representative(s) gives consent (if allowed according to local requirements), the subject must be informed about the study to the extent possible given his/her understanding. If the subject is capable of doing so, he/she must indicate agreement by personally signing and dating the written informed consent document.

Informed consent must be obtained before conducting any study-specific procedures (e.g. all of the procedures described in the protocol). The process of obtaining informed consent must be documented in the subject source documents.

Novartis will provide to investigators in a separate document a proposed informed consent form that complies with the ICH GCP guidelines and regulatory requirements and is considered appropriate for this study. Any changes to the proposed consent form suggested by the investigator must be agreed by Novartis before submission to the IRB/IEC.

Information about common side effects already known about the investigational drug can be found in the Investigator's Brochure (IB) . This information will be included in the subject informed consent and should be discussed with the subject during the study as needed. Any new information regarding the safety profile of the investigational drug that is identified between IB updates will be communicated as appropriate, for example, via an investigator notification (IN) or an aggregate safety finding. New information might require an update to the informed consent and then must be discussed with the subject.

Women of child bearing potential must be informed that taking the study treatment may involve unknown risks to the fetus if pregnancy were to occur during the study and agree that in order to participate in the study they must adhere to the contraception requirements.

Male subjects must be informed that if a female partner becomes pregnant while he is enrolled in the study, contact with the female partner will be attempted to request her consent to collect pregnancy outcome information.

A copy of the approved version of all consent forms must be provided to Novartis after IRB/IEC approval.

## **8 Visit schedule and assessments**

The Assessment Schedule lists all of the assessments when they are performed. All data obtained from these assessments must be supported in the subject's source documentation.

Subjects should be seen for all visits/assessments as outlined in the assessment schedule or as close to the designated day/time as possible. Missed or rescheduled visits should not lead to automatic discontinuation. Subjects who prematurely discontinue the study for any reason other than withdrawal of consent should be scheduled for a visit as soon as possible, at which time all of the assessments listed for the final visit will be performed. At this final visit, all dispensed investigational product should be reconciled, and the adverse event and concomitant medications recorded on the CRF.

Allowed visit windows are specified as follows:

- When dose modification, each visit must be completed  $\pm$  3 day until dose stabilization,
- Until stabilization of dose, each visit must be completed  $\pm$  3 day,
- After stabilization of dose, each visit must be completed  $\pm$  7 day,
- The efficacy assessment visit (week 13, 26 and 52) must be completed  $\pm$  3 day,
- The safety follow-up visit must be completed  $\pm$  7 day.

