### **6.5.2 Follow-up for toxicities**

Subjects whose treatment is interrupted or permanently discontinued due to an adverse event or clinically significant laboratory value, must be followed up at least once a week (or more frequently if required by institutional practices, or if clinically indicated) for 4 weeks, and subsequently at approximately 4-week intervals, until resolution or stabilization of the event, whichever comes first. Appropriate clinical experts such as ophthalmologist, endocrinologist, dermatologist, psychiatrists etc. should be consulted as deemed necessary.

All subjects must be followed up for adverse events and serious adverse events for 30 days following the last doses of eltrombopag.

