## **9.2 Study completion and post-study treatment**

Study completion is defined as when a subject finishes her/his Study Completion visit, and any repeat assessments associated with this visit have been documented and followed-up appropriately by the Investigator, or in the event of an early study termination decision, the date of that decision.

All treated subjects should have a safety follow-up visit conducted 30 days after last administration of study treatment. The information collected is kept as source documentation. All SAEs reported during this time period must be reported as described in [Section 10.1.3](#). Documentation of attempts to contact the subject should be recorded in the source documentation.

The primary analysis will be performed after all patients have completed Week 26 or discontinued prior to Week 26. The primary analysis data will be summarized in the primary clinical study report (CSR). Following the cut-off date for the analysis reported in the primary CSR, the study will remain open. Ongoing subjects will continue to receive study treatment and be followed as per the schedule of assessments, as long as subjects derive benefit from eltrombopag. An updated analysis will be conducted when all ongoing subjects complete 1 year (52 weeks) treatment. The efficacy and safety data till the cut-off date will be analyzed and summarized in the updated CSR.

The end of study defined as the earliest occurrence of one of the following:

1. All subjects have died or discontinued from the study.
2. Another clinical study becomes available that can continue to provide eltrombopag in this subject population and all subjects ongoing are eligible to be transferred to that clinical study.
3. When eltrombopag for the refractory and relapsed SAA is launched in China and available for the subjects.

The final analysis will occur at the end of the study. All available data from all subjects up to this cut-off date will be analyzed and summarized in a final CSR.

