## **10 Safety monitoring and reporting**

### **10.1 Definition of adverse events and reporting requirements**

#### **10.1.1 Adverse events**

An adverse event (AE) is any untoward medical occurrence (e.g. any unfavorable and unintended sign [including abnormal laboratory findings], symptom or disease) in a subject or clinical investigation subject after providing written informed consent for participation in the

study. Therefore, an AE may or may not be temporally or causally associated with the use of a medicinal (investigational) product.

The investigator has the responsibility for managing the safety of individual subject and identifying adverse events.

Novartis qualified medical personnel will be readily available to advise on trial related medical questions or problems.

The occurrence of adverse events must be sought by non-directive questioning of the subject at each visit during the study. Adverse events also may be detected when they are volunteered by the subject during or between visits or through physical examination findings, laboratory test findings, or other assessments.

Adverse events must be recorded in the Adverse Events CRF under the signs, symptoms or diagnosis associated with them, accompanied by the following information (as far as possible) (if the event is serious refer to [Section 10.1.2](#)):

1. The Common Toxicity Criteria (CTC) AE grade (version 4.03 or higher). Grade 1 to 5 will be used to characterize the severity of the Adverse Event. All grade 4 or higher value on Laboratory/investigational finding will be considered a medically significant event.
2. its relationship to the study treatment. If the event is due to lack of efficacy or progression of underlying illness (i.e. progression of the study indication) the assessment of causality will usually be 'Not suspected'. The rationale for this guidance is that the symptoms of a lack of efficacy or progression of underlying illness are not caused by the trial drug, they happen in spite of its administration and/or both lack of efficacy and progression of underlying disease can only be evaluated meaningfully by an analysis of cohorts, not on a single subject
3. its duration (start and end dates) or if the event is ongoing, an outcome of not recovered/not resolved must be reported.
4. whether it constitutes a SAE (see [Section 10.1.2](#) for definition of SAE) and which seriousness criteria have been met
5. action taken regarding with study treatment.

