All adverse events must be treated appropriately. Treatment may include one or more of the following:

- Dose not changed
- Dose Reduced/increased
- Drug interrupted/withdrawn
- 6. its outcome
  - a. not recovered/not resolved;
  - b. recovered/resolved;
  - c. recovered/resolved with sequelae;
  - d. fatal; or unknown.

If the event worsens, the event should be reported a second time in the CRF noting the start date when the event worsens in toxicity. For grade 3 and 4 adverse events only, if

improvement to a lower grade is determined a new entry for this event should be reported in the CRF noting the start date when the event improved from having been Grade 3 or Grade 4.

Conditions that were already present at the time of informed consent should be recorded in medical history of the subject.

Adverse events (including lab abnormalities that constitute AEs) should be described using a diagnosis whenever possible, rather than individual underlying signs and symptoms.

Adverse event monitoring should be continued for at least 30 days following the last dose of study treatment.

Once an adverse event is detected, it must be followed until its resolution or until it is judged to be permanent (e.g. Continuing at the end of the study), and assessment must be made at each visit (or more frequently, if necessary) of any changes in severity, the suspected relationship to the interventions required to treat it, and the outcome.

Information about adverse drug reactions for the investigational drug can be found in the Investigator's Brochure (IB).

Abnormal laboratory values or test results constitute adverse events only if they fulfill at least one of the following criteria:

- they induce clinical signs or symptoms
- they are considered clinically significant
- they require therapy

Clinically significant abnormal laboratory values or test results must be identified through a review of values outside of normal ranges/clinically notable ranges, significant changes from baseline or the previous visit, or values which are considered to be non-typical in subjects with the underlying disease.

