### **10.1.3 SAE reporting**

To ensure subject safety, every SAE, regardless of causality, occurring after the subject has provided informed consent and until 30 days following the last administration of study treatment must be reported to Novartis within 24 hours of learning of its occurrence. Detailed instructions regarding the submission process and requirements are to be found in the investigator folder provided to each site. SAEs occurring after the subject has provided informed consent until the time the subject is deemed a Screen Failure must be reported to Novartis.

All follow-up information for the SAE including information on complications, progression of the initial SAE and recurrent episodes must be reported as follow-up to the original episode within 24 hours of the investigator receiving the follow-up information. An SAE occurring at a different time interval or otherwise considered completely unrelated to a previously reported

one must be reported separately as a new event. SAEs will be followed until resolution or until clinically relevant improvement or stabilization.

If the SAE is not previously documented in the Investigator's Brochure or Package Insert (new occurrence) and is thought to be related to the study treatment, a Chief Medical Office and Patient Safety (CMO&PS) Department associate may urgently require further information from the investigator for health authority reporting. Novartis may need to issue an Investigator Notification (IN) to inform all investigators involved in any study with the same study treatment that this SAE has been reported.

Suspected Unexpected Serious Adverse Reactions (SUSARs) will be collected and reported to the competent authorities and relevant Ethics Committees (EC) in accordance with Europe (EU) Guidance 2011/C 172/01 or as per national regulatory requirements in participating countries.

Any SAEs experienced after the 30 day period following the last administration of study treatment should only be reported to Novartis Safety if the investigator suspects a causal relationship to study treatment.

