2.8 Safety analyses

All safety analyses will be based on the safety set.

The safety summary tables will include on-treatment assessments collected no later than 30 days after last dose of study treatment (see definition in [Section 2.1.1](#)).

All safety assessments will be listed by patient and flagged appropriately.

All safety assessments will be generated for the final CSR except for subgroup of interest.

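### A compliant safety follow-up visit on Days 23 to 29 leaves up to 7 of the 30 required adverse event days without scheduled questioning

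*Protocol*

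**What the plan says.** **Timing of the visit.** Protocol Section 9.2 states: "All treated subjects should have a safety follow-up visit conducted 30 days after last administration of study treatment". Table 8-1 places it at the same point. The list of allowed windows in Section 8 then gives this visit ("The safety follow-up visit must be completed") a tolerance of 7 days on either side.

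**Length of AE follow-up.** Section 6.5.2 says: "All subjects must be followed up for adverse events and serious adverse events for 30 days following the last doses of eltrombopag". Section 10.1.1 makes it a minimum: "Adverse event monitoring should be continued for at least 30 days following the last dose of study treatment". Section 10.1.3 sets the serious AE reporting period to run "until 30 days following the last administration of study treatment must be reported to Novartis within 24 hours" of the site learning of the event.

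**How AEs are found.** Section 10.1.1 ties active elicitation to visits: "The occurrence of adverse events must be sought by non-directive questioning of the subject at each visit during the study". It also accepts passive reports: "Adverse events also may be detected when they are volunteered by the subject during or between visits".

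**What is analysed.** Protocol 12.5.2 and SAP 2.1.3 end the on-treatment period 30 days after the last dose and start the post-treatment period the day after. Both select AEs for the summary tables by start date. For dated assessments SAP 2.8 says: "The safety summary tables will include on-treatment assessments collected no later than 30 days after last dose of study treatment".

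**The concern.** The AE tables report events with onset up to Day 30 after the last dose, and three protocol sections require follow-up for that long. Yet a site can hold the last scheduled visit a week earlier and be fully compliant. After that visit the documents name no further routine contact, neither a call nor a second visit, at which the subject would be asked about AEs.

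The subjects most exposed are those who stop for a reason other than an AE or a clinically significant laboratory value. Non-responders at Week 26 are the main planned group, since Sections 3 and 6.1.5 have them stop treatment. They do not receive the weekly contacts that Section 6.5.2 gives to subjects stopped for toxicity. At stake is whether AE counts for the last days of the on-treatment period rest on the same active questioning as the rest of the study.

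**Working it through.** The plan has no figure of its own to reproduce here. The check is a day count, with Day 0 as the day of the last dose.

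**Inputs**
- Nominal visit day: 30 (protocol 9.2, Table 8-1).
- Tolerance: 7 days either way (protocol 8).
- Required AE follow-up: 30 days (protocol 6.5.2, 10.1.1, 10.1.3).
- Last day of the on-treatment period: Day 30 inclusive (protocol 12.5.2, SAP 2.1.3).

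**Permitted visit days.** 30 − 7 = 23 and 30 + 7 = 37.

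**Days with no scheduled questioning** = max(0, 30 − visit day).

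| Visit day | Days to Day 30 with no scheduled questioning | AE onset days covered by questioning | Dated assessments in summary tables? |
|---|---|---|---|
| 23 | 7 | 23 of 30 | Yes |
| 26 | 4 | 26 of 30 | Yes |
| 29 | 1 | 29 of 30 | Yes |
| 30 | 0 | 30 of 30 | Yes |
| 31 | 0 | 30 of 30 | No, listed and flagged |
| 37 | 0 | 30 of 30 | No, listed and flagged |

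**Largest gap.** 7 / 30 = 23.3% of the required period, at a Day 23 visit. The range of 1 to 7 days for Days 23 to 29 needs no assumption about how visits are spread.

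**Late visits and AEs.** Inclusion follows the AE start date, so an event starting on Day 28 and recorded on Day 35 stays in the tables. Only onsets on Days 31 to 37 fall outside, as the on-treatment definition intends.

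**Late visits and dated assessments.** The legible rows of Table 8-1 show vital signs, the blood smear and a source-only physical examination at follow-up. Body weight and ECG end at the end-of-treatment visit, and SAP 2.8.4.3 only lists the smear. Among these rows, vital signs are therefore the only measurement that leaves a summary table when the visit falls after Day 30. The laboratory rows are not legible in the text available, so nothing is claimed about them.

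**Who is exposed.** Section 6.5.2 gives weekly contact for 4 weeks (4 × 7 = 28 days) to subjects stopped for an AE or a clinically significant laboratory value, which largely covers them. For the others, take the 40% response rate used in protocol 12.8.1: 20 × (1 − 0.40) = 12 subjects would be non-responders at Week 26. That is an upper figure for this group, because some of the 12 would have stopped earlier, possibly for an AE. It counts subjects who could be affected, not subjects who would be.

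**The case against.** The best reply is that the 30-day duty does not depend on the visit. Sections 6.5.2, 10.1.1 and 10.1.3 bind the investigator to Day 30 whenever the visit falls, and volunteered reports between visits count. Section 8 also asks for visits as close to the designated day as possible, so most should fall near Day 30. On the protocol's half-life of 21 to 32 hours (Section 1.3), Day 23 is at least 17 half-lives after the last dose (23 × 24 / 32 = 17.25), so events in the last week are unlikely to reflect remaining drug. All of this stands, and it makes the point an operational gap rather than a contradiction. It does not close the gap: AE follow-up is required regardless of cause, and a passive report does not replace the active questioning that Section 10.1.1 demands.

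Three stronger readings are tempting but unsupported.

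- *A late visit removes data from the AE tables.* The SAP 2.8 sentence about assessments collected by Day 30 might suggest this. Protocol 12.5.2 and SAP 2.1.3 select AEs by start date, so it does not.
- *The vital signs of a late visit are lost, and the on-treatment summaries should be extended to Day 37.* These values remain in the listings with a flag. Leaving them out of the tables follows a definition that protocol and SAP share. Extending it would depart from protocol 12.5.2. The Day 30 limit is itself reasonable, at 22.5 half-lives or more (30 × 24 / 32 = 22.5).
- *A known share of subjects will have an early visit.* An even spread over the permitted days would give one, but no document states a visit-timing distribution, and Section 8 points away from an even spread.

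**Conclusion.** The point holds as a minor inconsistency between the visit schedule and the AE follow-up requirement. A compliant visit on Days 23 to 29 leaves 1 to 7 of the 30 required days, at most 23%, without scheduled AE questioning. This applies to subjects not stopped for an AE or a clinically significant laboratory value. It rests on one reading: that no routine contact is planned after the follow-up visit, since none is named in the legible part of Table 8-1 or in Sections 8, 9.1.1, 9.2 or 10.1. Late visits need no correction.

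The number of subjects affected cannot be derived from the documents, and not everyone who stops reaches this visit, because of deaths, withdrawn consent and loss to follow-up. The possible effect is some under-recording of AEs with onset late in the on-treatment period. The primary endpoint is unaffected.

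**What to change.** Reconcile the follow-up window in protocol Section 8 with Sections 6.5.2, 10.1.1 and 10.1.3 so that scheduled AE questioning always reaches Day 30. The simplest way is to let the window run forward only, from Day 30 to Day 37. An alternative is to keep the present window and require an AE contact on or after Day 30 whenever the visit took place earlier. The SAP on-treatment definition stays as it is.

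The forward-only window changes one line and adds no visit. It has three costs:
- Subjects who would have come early come later, by 7 days for someone moved from Day 23 to Day 30. The latest permitted day stays Day 37.
- Sites have 8 permitted days instead of 15.
- More visits may fall after Day 30, where vital signs are listed but not summarised.

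The alternative avoids these costs but adds one contact for each early visit. For visits already held, a listing of the follow-up day relative to the last dose would show how many subjects have a gap and how long it is.

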**Table 8-1 Assessment Schedule**

Visit Name	Screening	Treatment							End of Study	
		Day 1	Week 1/2/3	Week 4	Week 5 to 51 (Every 2 weeks until stabilization of dose; every 4 weeks, after stabilization of dose) 	Week 13	Week 26/52	Extension part (Every 2 weeks until stabilization of dose; every 4 weeks after stabilization of dose) 	End of treatment	Follow-up (30 days after treatment discontinuation)
Days	-30 to -1	1 to 1	8 to 22	29 to 29	36 to 358	92	183 to 365	After Week 52	EOT	after EOT
Informed consent	X									
Demography	X									
Medical history/current medical conditions	X									
Characteristics of SAA	X									
Inclusion / Exclusion criteria	X									
Supportive therapy	X	X	X	X	X	X	X	X	X	X
Concomitant medications	X	X	X	X	X	X	X	X	X	X
Physical Examination	S	S	S	S	S	S	S	S	S	S
Vital Signs	X	X		X	Once a month	X	X	Once a month	X	X
Height	X									
Body Weight	X						X		X	
Standard 12 lead ECG	X						X	Once in 6 months (Example: Weeks 78, 104...)	X	
Adverse Events	X	X	X	X	X	X	X	X	X	X
Peripheral blood smear	X	X	X	X	X	X	X	X	X	X
Bone marrow aspiration (iliac crest) and cytogenetic analysis	Within 3 months of Day 1					X	X	Once in 6 months (Example: Weeks 78, 104...)	Not necessary if conducted within 6 months.	

Period	Screening	Treatment								End of Study	
Visit Name	Screening	Day 1	Week 1/2/3	Week 4	Week 5 to 51 (Every 2 weeks until stabilization of dose; every 4 weeks, after stabilization of dose) 	Week 13	Week 26/52	Extension part (Every 2 weeks until stabilization of dose; every 4 weeks after stabilization of dose) 	End of treatment	Follow-up (30 days after treatment discontinuation)	
Days	-30 to -1	1 to 1	8 to 22	29 to 29	36 to 358	92	183 to 365	After Week 52	EOT	after EOT	
assessment											
Evaluation of clonal evolution to AML and MDS	X	When clinically indicated.									
PK blood sampling		Intensive PK in 12 subjects (pre-dose, 1, 2, 4, 6, 8, and 24 h post-dose) on day 14 after initial dose; Sparse PK in all subjects: Pre-dose on day 15 after initial dose and pre-dose on day 15 after each new dose has started (dose escalation only)									
Prescription of eltrombopag		Eltrombopag will be distributed every 2 weeks or every 4 weeks after stabilization of dose according to Section 6.5									
Treatment compliance			S	S	S	S	S	S	S		
Disposition	X									X	X

X Assessment to be recorded in the clinical database or received electronically from a vendor

S Assessment to be recorded in the source documentation only

 "Until stabilization of dose" means that the dose is not changed for at least 4 weeks. If the dose is changed at visiting every 4 weeks, the subject should visit hospital since the next visit until stabilization of dose.

